8.6.3. Vital Signs

Vital sign measurements (heart rate, blood pressure [systolic and diastolic], and respiratory rate) and changes from baseline values will be summarized by study visit. Height, weight, and BMI will be summarized. Individual profile of weight and BMI over time will be plotted. Individual subject listing of vital signs will be provided.

8.6.4. Electrocardiogram

Each ECG will be interpreted as "normal", "abnormal not clinically significant", or "abnormal clinically significant" by the study investigator and captured on eCRF. Shift from baseline in ECG interpretation will be summarized at Week 52/EOS. The interpretation of the ECG data will be listed by study visit.

A listing of ECG results will be provided.

8.6.5. Liver Ultrasound

An ultrasound of the liver will be conducted during the screening period. Ultrasound results will be provided in a listing.

8.6.6. Symptomatic Hypoglycemic Events

The number of subjects who reported symptomatic hypoglycemic events will be summarized by study visit. Symptomatic hypoglycemic events resulting in a visit to the emergency room or hospitalization are also reported as AEs on AE eCRF.

Details of the symptomatic hypoglycemic events will be provided in a listing.

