
Study Methodology:
	
Screening Period
 
After a subject has provided written informed consent and within the 56 days prior to Day 0, the Investigator or other qualified study personnel will determine if the subject is eligible for the study. This will be accomplished by reviewing the inclusion and exclusion criteria and completing all of the screening assessments. Screening assessments may be performed on more than 1 day; all assessments must be completed and results available and reviewed within the 56-day Screening Period prior to Day 0.
 
Screening assessments include recording of the following: demographic data; medical and GSDIa history; prior medications, therapies, and procedures; vital sign measurements; and height and weight. A 12-lead electrocardiogram (ECG) and a complete physical examination will be performed. Blood samples will be collected for hepatitis B virus, hepatitis C virus, and human immunodeficiency virus status; serum pregnancy testing (for females of childbearing potential only); G6PC genotyping; AAV8 neutralizing antibody testing; AAV8 binding antibody immunoglobulin G (IgG) testing; and clinical laboratory assessments (clinical chemistry [including liver function tests], hematology, and coagulation panel). It is recommended that blood samples for G6PC genotyping and AAV8 neutralizing antibody testing be collected at the time written informed consent is provided. A urine sample will be collected for urinalysis.
 
An ultrasound of the liver will be performed. Adverse events and SAEs will be monitored after the subject has provided written informed consent. The number of symptomatic hypoglycemic events with documented glucose of < 60 mg/dL (< 3.0 mmol/L) that occurred during the previous 52 weeks will be recorded. The subject’s daily prescribed diet, daily diet intake, daily prescribed cornstarch (or equivalent), and daily cornstarch (or equivalent) intake will be recorded during scheduled study visits and, if possible, on a weekly basis through the Week 52 visit or early withdrawal.
 
The site will provide copies of the GSDIa Morning Diary and GSDIa Evening Diary to subjects and instruct them to bring the completed assessments to the Day 0 and Weeks 12, 24, and 52 visits.
 
The site will provide a continuous glucose monitoring (CGM) device to the subject after determining that the subject is eligible for the study. Subjects will be educated on the

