### **3.2.3. Follow-up Period**

Subjects will be asked to visit the study site at a minimum of every 3 to 4 days through Week 12, or longer if clinically indicated (Table 6). Following the Week 12 visit, subjects will visit the

study site approximately once every 12 weeks through Week 36 and at Week 52 or their early withdrawal from the study (Table 6).

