### **3.2.3.1. Outpatient Study Site or Home Visits**

Subjects will be asked to provide clinical laboratory samples at a minimum of every 3 to 4 days through Week 12 of the study, or longer if clinically indicated (Table 6). Subjects may have the option of having these samples collected at their homes by clinically trained and qualified personnel (if arranged by the Investigator), unless there is a scheduled study site visit that the subject must attend in person (Table 6).

During these visits, a blood sample will be collected for determination of clinical chemistry (including liver function tests) and sent to the central laboratory. A second blood sample will be collected for liver function tests and sent to the local laboratory (STAT sample; Section 8.2.6.2). Saliva, urine, and stool samples will also be collected during these visits for assessment of vector shedding until at least 3 consecutive negative results are obtained from each sample matrix (Section 8.2.6.10). A blood sample will be collected for determination of cell-mediated immune response to AAV8 and G6Pase testing approximately weekly (Section 8.2.6.7).

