#### **8.2.5. Hypoglycemic Events**

At each visit, the study site will instruct subjects on proper home glucose monitoring, the signs and symptoms of hypoglycemia, and supplemental glucose treatment if needed. During Screening, the study site will record the number of symptomatic hypoglycemic events that occurred during the previous 52 weeks in the eCRF. During each subsequent visit, the study site will record the number of symptomatic hypoglycemic events that occurred since the last visit in the eCRF (Table 6).

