#### **10.2.4.5. Hypoglycemic Events**

The number of symptomatic hypoglycemic events will be summarized by dose level of DTX401. Hypoglycemic events reported by the subject will be summarized separately for each dose of DTX401.

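### SAP 8.6.6 counts subjects with symptomatic hypoglycemia by visit over unequal look-back periods, so the visits are not comparable and the protocol's event counts by dose are lost

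*SAP*

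**What the plan says.** **What is collected.** Protocol Section 8.2.5 has the site record counts of events, over two kinds of period. "During Screening, the study site will record the number of symptomatic hypoglycemic events that occurred during the previous 52 weeks in the eCRF". After that, "During each subsequent visit, the study site will record the number of symptomatic hypoglycemic events that occurred since the last visit in the eCRF".

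**What the protocol plans to report.** Section 10.2.4.5: "The number of symptomatic hypoglycemic events will be summarized by dose level of DTX401".

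**What the SAP plans to report.** Section 8.6.6: "The number of subjects who reported symptomatic hypoglycemic events will be summarized by study visit". A listing gives the details of the events. Under SAP Section 8.1, tables are shown by scheduled visit, without analysis windows, by dosing cohort and overall. SAP Section 9, on changes from the protocol's analyses, reads only: None.

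**When visits occur.** Screening falls "within the 56 days prior to Day 0", according to the synopsis. For the outpatient or home visits, protocol Section 3.2.3.1 states: "Subjects will be asked to provide clinical laboratory samples at a minimum of every 3 to 4 days through Week 12". After Week 12, Section 3.2.3 brings subjects to the "study site approximately once every 12 weeks through Week 36 and at Week 52 or their early withdrawal from the study". The site visits after dosing are at Weeks 4, 6, 12, 24, 36 and 52.

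**The concern.** The chance that a subject reports at least one event grows with the length of time asked about. A table of subjects with any event, laid out by visit, therefore mixes the event rate with the spacing of visits. The look-back is a year at Screening and ranges from weeks to months afterwards, so the proportions would differ between visits even if DTX401 did nothing.

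Hypoglycemia is the central manifestation of this disease, and symptomatic events are a named safety assessment. Readers will be inclined to read such a table across its columns.

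The statistic has also changed without being declared. The protocol promises a number of events by dose level. The SAP gives a number of subjects by visit and cohort. The event counts would appear only in a listing, with no summary that puts them over the time at risk.

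**Working it through.** The documents give no expected rate and no figure for this summary, so there is nothing to reproduce. The check asks what the planned table would show if the event rate never changed.

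**Look-back lengths (days)**
- Screening: 52 × 7 = 364.
- Day 0: up to 56. Day 1 predose: about 1.
- Post-dose, site visits only (Days 1, 28, 42, 84, 168, 252, 364): differences 27, 14, 42, 84, 84, 112.
- Post-dose, if outpatient or home visits also count: 3 to 4 days up to Week 12, then 84, 84, 112.

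Which post-dose set applies is open. Section 8.2.5 refers to each subsequent visit. The assessments described for the outpatient or home visits in Section 3.2.3.1 and the synopsis do not include hypoglycemic events, and that row of the Schedule of Events (protocol Table 6) is not readable in the copy available here.

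**Formula.** With a constant rate L per subject-year (Poisson) and a look-back of t days, P(at least one event) = 1 − exp(−L × t / 364). The rate L is an assumption. For example, at L = 2 and t = 84: 1 − exp(−2 × 84/364) = 1 − exp(−0.4615) = 0.370.

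| Look-back | L = 0.5 | L = 2 | L = 12 |
|---|---|---|---|
| 364 d (Screening) | 39.3% | 86.5% | 100.0% |
| up to 56 d (Day 0) | 7.4% | 26.5% | 84.2% |
| 27 d (Week 4) | 3.6% | 13.8% | 58.9% |
| 14 d (Week 6) | 1.9% | 7.4% | 37.0% |
| 42 d (Week 12) | 5.6% | 20.6% | 75.0% |
| 84 d (Weeks 24, 36) | 10.9% | 37.0% | 93.7% |
| 112 d (Week 52) | 14.3% | 46.0% | 97.5% |
| 4 d (only if home visits count) | 0.5% | 2.2% | 12.4% |

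At L = 2, the expected numbers among 12 subjects are 10.4 at Screening, 0.9 at Week 6, 4.4 at Week 24 and 5.5 at Week 52.

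**Direction.** At L = 2, Screening to Week 24 looks like a fall (86% to 37%). Week 6 to Week 52 looks like a rise (7% to 46%). So does Day 0 to Week 52 (at most 26.5%, to 46%), and Day 0 is nearer the SAP's own definition of baseline as the last pre-dose assessment (Section 5.1).

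**Sensitivity to unequal subjects.** With negative binomial counts (k = 0.5), P = 1 − (1 + L × t / (364k))^(−k). At L = 2 this gives 55% at Screening, 7% over 14 days, 28% over 84 days and 33% over 112 days. The pattern is flatter but remains. At L = 12 it gives 80%, 28%, 61% and 66%.

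**Equal windows.** Pooling Day 1 to Week 52 gives 363 days against 364 before Screening. The proportions with any event are then 63.1% and 63.2% at L = 1, and 98.1% and 98.2% at L = 4. As events per subject-time, the expected ratio under no effect is 1.0.

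**The case against.** The case for leaving the table alone has real substance.

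- **The events are not discarded.** Section 8.6.6 lists them, and with 12 subjects in cohorts of 3 each event can be inspected. Events leading to an emergency visit or hospitalization are also adverse events, and the tables by system organ class and preferred term in SAP 8.6.1 count events as well as subjects. For Cohorts 3 and 4, continuous glucose monitoring counts low-glucose episodes weekly, though not by symptoms. This stands. What is missing is a summary of the symptomatic event counts over time at risk.
- **Dose is partly recoverable.** Cohort 1 is Dose 1 and Cohorts 2 to 4 are Dose 2. This also stands, but the table gives subjects rather than events, and no pooled Dose 2 column is specified.
- **A before-after comparison has its own biases.** The earlier year rests on recall. Follow-up includes fasting challenges that can end with hypoglycemic symptoms, and the documents do not say whether those events are counted. Steroids are given only at or after dosing. A per-subject rate ratio is undefined when the earlier count is zero. These points shape the fix; they do not make the by-visit table comparable.

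A reader might go further and infer that the table must show a large drop after dosing, with look-backs as short as 4 days. The documents do not support that. The 4-day interval rests only on the general wording of Section 8.2.5. A drop needs Screening as the comparator, and the SAP plans no change from baseline for these events. Its size depends on a rate that the documents do not give. Under the Poisson model at 12 events per subject-year or more, the difference between Screening and the visits with 12- to 16-week look-backs nearly vanishes.

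**Conclusion.** The point holds as one of non-comparability and of an undeclared change in the reported statistic. Followed as written, SAP 8.6.6 produces by-visit proportions that differ with no treatment effect, because the look-back is 364 days at Screening and, on the site-visit reading, 14 to 112 days at Week 4 and later. At an assumed 2 events per subject-year the no-effect proportions run from 7% to 86%. The sizes rest on a constant assumed rate, and the direction depends on the visits compared. Shorter look-backs would widen the range, but await confirmation that events are recorded at outpatient or home visits.

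Separately, the protocol's number of events by dose level has become a number of subjects by visit, so the entry in SAP Section 9 is inaccurate. The consequence is confined to a descriptive safety summary: no test, sample size or input to the continual reassessment method is affected. The change should be made but is not critical.

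**What to change.** In SAP 8.6.6:

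1. Summarize the number of events, the number of subjects affected and events per subject-year, for the 52 weeks before Screening and for dosing to Week 52 or withdrawal. Show these by subject, by cohort and by dose, with Dose 2 pooled over Cohorts 2 to 4.
2. Describe within-subject change as a rate difference, not a per-subject ratio.
3. Show events during controlled fasting challenges separately.
4. Footnote that the period before Screening relies on recall.
5. State the look-back length for each visit in any by-visit table, and confirm whether events are recorded at outpatient or home visits.
6. Keep the listing, and record in Section 9 any departure from the protocol that remains.

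The cost is SAP wording and one descriptive table. The counts are already collected; separating the fasting-challenge events depends on their being identifiable from the recorded event details and challenge times.

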8.6.7. Clinical Laboratory Assessments

Clinical laboratory assessments are mainly collected at central laboratory (Table 2), except for data collected during CFC which is collected at local laboratory and analyzed as described in Section 8.5.1. For all central clinical laboratory parameters (Table 2) with continuous results, absolute values and changes from baseline will be summarized by study visit. For central laboratory parameters with categorical results, results will be included in a listing because these parameters are either non-critical for analysis (e.g., Urinalysis blood (by dipstick), or microscopic examination parameters, etc.) or they are collected only at screening visit (e.g., HBV surface antigen).

Listings of laboratory parameters will be provided. Individual patient profile of triglyceride with daily cornstarch intake over time will be plotted.

Table 2: Central Clinical Laboratory Parameters

Clinical chemistry:	Lipid panel, uric acid, sodium, potassium, chloride, carbon dioxide, blood urea nitrogen, creatinine, glucose, calcium, phosphate, magnesium, albumin, total protein, creatine kinase, bilirubin (total, direct, and indirect), ALT, AST, ALP, gamma-glutamyl transferase, and lactate dehydrogenase
Hematology:	Complete blood count with differential
Urinalysis:	Specific gravity, pH, glucose, protein, blood (by dipstick), ketones (by dipstick), and microscopic examination (if blood or protein is found)
Other:	HBV surface antigen, HCV RNA, HIV,
(collected only at Screening)	
Coagulation panel:	PT/INR, aPTT
24-Hour urine:	Total protein, microalbumin, and creatinine

Abbreviations: ALP = alkaline phosphatase; ALT = alanine aminotransferase; aPTT = activated partial thromboplastin time; AST = aspartate aminotransferase; HBV = hepatitis B virus; HCV = hepatitis C virus; HIV = human immunodeficiency virus; PT/INR = prothrombin time/international normalized ratio.

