### 8.2.6.2. Elevation of Liver Function Tests

In clinical studies with AAV-mediated gene transfer, a transient increase in liver aminotransferases and a concurrent decline in transgene expression have been observed (Manno et al., 2006; Nathwani et al., 2011b; Nathwani et al., 2014). This has been hypothesized to be due to the activation of capsid-specific cytotoxic T lymphocytes and destruction of transduced liver cells (Mingozzi et al., 2007). However, in mice, T cells activated against AAV capsid were not able to target and eliminate transduced hepatocytes (Wang et al., 2007; Li et al., 2007a; Li et al.,

2007b; Siders et al., 2009) unless the transduced hepatocytes co-expressed the wild-type AAV capsid protein (Li et al., 2007a).

The inability to reproduce the observed effects in animal models has made it difficult to assess the validity of the hypothesis or to develop strategies to overcome or minimize aminotransferase elevations. Despite a lack of clear resolution that activation of cytotoxic T lymphocytes leads to a reduction in transgene expression from hepatocytes, appropriate precautions have been incorporated into this study. In addition to monitoring for capsid-specific and G6Pase-specific T-cell activation, subjects will receive oral steroid treatment for possible vector-induced hepatitis if liver function tests increase following treatment with DTX401 as outlined in Section 8.2.6.2.1. Subjects in Cohort 4 will receive prophylactic oral steroid treatment to prevent possible vector-induced hepatitis as outlined in Section 8.2.6.2.2.

Liver function tests will be assessed as part of clinical chemistry (Section 8.2.6.1) at the time points specified in the Schedule of Events (Table 6). Liver function tests will be assessed at the central laboratory and the local laboratory (STAT sample) at a minimum of every 3 to 4 days through Week 12, or longer if clinically indicated, to allow for a rapid detection of any liver aminotransferase elevations following administration of DTX401. An increase in liver function tests following treatment with DTX401 will be recorded as an AE or SAE, as defined in Section 9.1.2, on the appropriate pages of the eCRF if it is felt to be clinically significant in the medical and scientific judgment of the Investigator.

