#### **10.2.4.6. Clinical Laboratory Assessment Results**

For all clinical laboratory parameters (Section 8.2.6.1) with continuous results, absolute values and changes from Baseline will be summarized by visit and dosing cohort. For laboratory parameters with categorical results, shifts from Baseline will be summarized by visit and dosing cohort. Laboratory values from the central laboratory and local laboratories will be analyzed.

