STATISTICAL ANALYSIS PLAN (SAP)

Title: A Phase 1/2, Open-Label Safety and Dose-Finding Study of

Adeno-Associated Virus (AAV) Serotype 8 (AAV8)-Mediated Gene Transfer of Glucose-6-Phosphatase (G6Pase) in Adults

with Glycogen Storage Disease Type Ia (GSDIa)

Protocol: 401GSDIA01

Investigational Product: DTX401 (Nonreplicating, recombinant AAV8 vector that

contains a codon-optimized, human G6PC coding sequence)

Phase: 1/2

Sponsor: Ultragenyx Pharmaceutical Inc.

[name]

[name]

Author:

Senior Director, Biostatistics, Biometrics

Director, Biostatistics, Biometrics

Date: 12 July 2021

Date Amended: 04 March 2022

Version Number: Version 2.0

CHANGE HISTORY

Version	Changes and Rationale for Changes
1.0	Initial Version
2.0	Minor changes in the document include changes to match the language in the SAP with the corresponding language in the protocol, removing redundancy in analyses that were described multiple times in the document, and adding clarifications around endpoint or analysis.
	Major changes in the document are summarized below.
	Section 3.7:
	Added update on latest data monitoring committee (DMC) conducted for the study
	 Removed text about the roles and responsibilities of the DMC because that is outside the scope of the SAP.
	Section 8.4.1: Added derivation of actual dose administered to the subject
	Section 8.5.1: Added summary of cornstarch used and amount of carbohydrates in the dinner prior to controlled fasting challenge (CFC) upon request from medical monitor to understand use of these quantities in CFC.
	Section 8.5.2 : Added analysis window for analysis of cornstarch data. Added plot for daytime, bedtime, and nighttime frequency of cornstarch doses.
	Section 8.5.3:
	 Added exploratory analyses of continuous glucose monitoring (CGM) data based on the request from medical monitor of the study to gain better understanding of this data.
	 Added derivation for percentage of time spent in any glucose range in a week
	 Removed text about the use of both Cenduit and Clarity data for analysis of CGM data because Clarity data will not be part of clinical dataset.
	Section 8.6.7: Removed reference of few safety labs parameters from this section because analyses planned for these parameters are already described in other sections. Further, clarified that this section focuses on analyses for lab parameters collected at the central lab.

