8. STATISTICAL METHODS OF ANALYSES

8.1. General Principles

Continuous variables will be summarized by number of subjects and mean, standard deviation (SD), standard error (SE), median, Q1, Q3, minimum, and maximum values. Categorical variables will be summarized by number and percentage of subjects. All summary tables will be presented by scheduled study visit and no analysis windows will be used, unless specified otherwise. All the summary tables will be presented by dosing cohort of DTX401 and overall, unless specified otherwise. The dosing cohorts are:

- Cohort 1: Dose 1 $(2.0 \times 10^{12} \,\text{GC/kg})$ with a reactive steroid regimen (prednisone starting dose of 40 mg/day)
- Cohort 2: Dose 2 $(6.0 \times 10^{12} \,\text{GC/kg})$ with a reactive steroid regimen (prednisone starting dose of 40 mg/day)
- Cohort 3: Dose 2 $(6.0 \times 10^{12} \,\text{GC/kg})$ with an optimized reactive steroid regimen (prednisone starting dose of 60 mg/day)
- Cohort 4: Dose 2 $(6.0 \times 10^{12} \text{ GC/kg})$ with a prophylactic steroid regimen

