9. CHANGES TO ANALYSES SPECIFIED IN PROTOCOL

None

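### SAP 8.6.7 summarises only central laboratory results and SAP 8.1 only scheduled visits, so local STAT and unscheduled liver tests enter no laboratory table the SAP describes, although Protocol 10.2.4.6 says local values will be analysed

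*SAP*

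**What the plan says.** Protocol 8.2.6.2 sets up paired liver testing: "Liver function tests will be assessed at the central laboratory and the local laboratory (STAT sample"), at intervals of no more than 3 to 4 days up to Week 12 and beyond that if clinically indicated. Protocol 8.2.6.2.1 asks for any repeat test within 24 hours of a raised ALT result. Protocol 8.1.1 adds a local STAT AST and ALT on the morning of each fasting-challenge admission. On analysis, Protocol 10.2.4.6 says: "Laboratory values from the central laboratory and local laboratories will be analyzed".

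SAP 8.6.7 describes the data differently: "Clinical laboratory assessments are mainly collected at central laboratory (Table 2), except for data collected during CFC which is collected at local laboratory". The planned summary is: "For all central clinical laboratory parameters (Table 2) with continuous results, absolute values and changes from baseline will be summarized by study visit". The SAP change history shows that the scope was chosen on purpose; version 2.0 "clarified that this section focuses on analyses for lab parameters collected at the central lab". SAP 8.1 sets the default for tables: "All summary tables will be presented by scheduled study visit and no analysis windows will be used, unless specified otherwise". No exception is made for laboratory data. SAP 9, headed "CHANGES TO ANALYSES SPECIFIED IN PROTOCOL", reads None.

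The SAP also plans laboratory listings (8.6.7), an individual plot of ALT and prednisolone dose over time (8.6.7.1), and the usual AE tables (8.6.1).

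**The concern.** The SAP's account of which data are local leaves out the STAT liver tests, and its tabulation rule excludes both those tests and any liver test made outside a scheduled visit. That departs from Protocol 10.2.4.6, and SAP 9 does not declare it.

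Liver tests are the laboratory data for which this matters most. Protocol 1.3.1 treats the aminotransferase rise as the one identified adverse event of AAV gene transfer. Cohorts 3 and 4 share Cohort 2's dose and differ from it in steroid regimen, and Cohort 4 is enrolled if the Cohort 3 regimen does not control ALT rises well enough. To compare these regimens the reader needs each subject's ALT peak and its timing. By-visit means and changes from baseline in cohorts of 3 do not show that, and a peak recorded only on a repeat or clinically indicated sample would not enter them at all.

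**Working it through.** The plan gives no figure to reproduce. The check is a comparison of texts and a count of nominal days in the Schedule of Events.

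**1. What reaches a laboratory table**

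| Liver result | Protocol source | In a laboratory summary table under SAP 8.1 and 8.6.7? |
|---|---|---|
| Central, scheduled visit | 8.2.6.2 | Yes |
| Local STAT, scheduled visit | 8.2.6.2, 3.2.3.1 | No: not a central parameter |
| Local STAT on fasting-challenge admission | 8.1.1 | No: drawn before the challenge; SAP 8.5.1 lists parameters collected during it |
| Repeat test after a raised ALT | 8.2.6.2.1 | No, if outside a scheduled visit |
| Clinically indicated test after Week 12 | 8.2.6.2 | No, if outside a scheduled visit |

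SAP 8.5.2 has a rule that brings in unscheduled visits for cornstarch data. There is none for liver tests.

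**2. Through Week 12**

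The visit columns are Days 4, 8, 12, 16, 20, 24, 28, 32, 36, 39, 42, 45, 48, 52, 56, 60, 64, 68, 72, 76, 80 and 84. That is 22 visits, each 3 or 4 days after the one before, which matches the stated frequency. Each has a central sample that is tabulated, so ALT is densely sampled in the tables over this period. (The amendment history shows a 4- to 5-day interval before Version 5.0, so the count of 22 does not fit every cohort.)

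**3. After Week 12**

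The remaining scheduled visits are Weeks 24, 36 and 52, that is Days 168, 252 and 364.

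- Gaps: 168 − 84 = 84 days; 252 − 168 = 84 days; 364 − 252 = 112 days.
- Share of follow-up: (364 − 84)/364 = 280/364 = 77% of the days, covered by 3 of 22 + 3 = 25 scheduled post-dose visits.

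The protocol refers to an 8-week prophylactic prednisone regimen (the vaccination text following 8.2.6.2.2). For Cohort 4 this leaves about 12 − 8 = 4 weeks of dense scheduled sampling after the regimen ends.

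**4. Illustration of the post-Week 12 exposure**

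Assumption: an ALT flare of L days lies wholly between Day 84 and Day 364, and its start is equally likely on any day in that span. The documents give no flare duration, so a range is shown. Visit windows are ignored. For L up to 84:

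P(no scheduled visit falls in the flare) = [(84 − L) + (84 − L) + (112 − L)] / (280 − L) = (280 − 3L)/(280 − L)

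| L (days) | Calculation | Probability |
|---|---|---|
| 14 | 238/266 | 0.895 |
| 28 | 196/252 | 0.778 |
| 42 | 154/238 | 0.647 |
| 56 | 112/224 | 0.500 |

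In those cases any ALT result from the flare would come from an unscheduled test and would be outside the laboratory tables.

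**5. Whether other outputs fill the gap**

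- *AE tables.* Protocol 8.2.6.2 and 9.1.3 send a liver-test rise to the AE page if the investigator judges it clinically significant. It is then graded by Table 4, whose criteria contain no ALT multiples. The AE grade therefore cannot recover the size of the peak.
- *Listings and ALT plot.* SAP 8.6.7 and 8.6.7.1 do not say whether local or unscheduled values are included.
- *Peak tables.* SAP 8.6.8 plans peak value and time of peak for each subject for vector genome copies. The SAP text describes no such table for ALT or AST.

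**The case against.** The strongest reply is that little of clinical importance would be lost. AE tables do not depend on which laboratory found the rise or whether the visit was scheduled, and Protocol 8.2.6 is broad, since it also counts results that worsen from baseline. The listings are not limited to central or scheduled data. With 12 subjects, an individual plot of ALT against steroid dose is arguably more informative than any visit summary. Keeping summaries to one laboratory with one reference range is defensible, SAP 8.6.7 says only that data are mainly central, and the protocol's promise to analyse local values does not require a by-visit table. The list of outputs is in a separate shell document (SAP 10), which may contain a maximum-ALT table.

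Much of this stands, and it rules out three stronger readings that a reader might infer:

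- *That the local results are the ones that trigger steroids.* Protocol 8.2.6.2.1 refers to a rise in ALT from baseline or recent levels and names no laboratory; SAP 8.6.7.1 refers to ALT above ULN and names none either. (Those two descriptions differ and must be reconciled, which is a separate matter.) Protocol 8.2.6.2 gives rapid detection as the purpose of central and local testing together.
- *That ALT peaks would go unreported.* AE tables, listings and the plot may carry them. What can be said is that they can be missing from the laboratory summary tables.
- *That 22 × 12 = 264 omitted STAT samples measure the loss.* Each is paired with a central sample that is tabulated, so the count says nothing about missed peaks.

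The reply does not remove the undeclared departure from Protocol 10.2.4.6, the incomplete description of local data, or the silence on whether listings and plot include local and unscheduled values.

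**Conclusion.** The point holds in limited form. As written, SAP 8.1 and 8.6.7 leave local STAT and unscheduled liver tests out of every laboratory summary table that the SAP describes, contrary to the plain sense of Protocol 10.2.4.6, and SAP 9 does not say so. Through Week 12 the effect is small because of the paired central samples. It is larger for repeat tests and for clinically indicated tests after Week 12, where scheduled visits are 84, 84 and 112 days apart. Under the uniform-placement assumption, a flare of 14 to 56 days in that period has a 90% to 50% chance of containing no scheduled visit. That range illustrates exposure; it does not estimate how many flares occur. The conclusion also assumes that the separate shell document adds no such table. The matter should be corrected because it bears on the comparison of steroid regimens, but it does not undermine the safety analysis as a whole.

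**What to change.** - **SAP 8.6.7:** correct the description of local data to include the STAT liver tests.
- **SAP 8.6.7 and 8.6.7.1:** state that the listings and the ALT/prednisolone plot include local and unscheduled results, with the laboratory source flagged.
- **SAP 8.6.7.1:** add one table, by subject and by cohort, of maximum post-dose ALT and AST through Week 52 from all results: multiple of that laboratory's ULN, multiple of baseline, day of peak, and laboratory source. Give a rule for paired central and local values from the same visit.
- **SAP 9:** declare any departure from Protocol 10.2.4.6 that remains.

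The cost is SAP wording and one table, in a format close to what SAP 8.6.8 already plans. It assumes that the local results are in the database, as Protocol 10.2.4.6 implies. The downside is that local reference ranges differ, so values must be scaled to each laboratory's ULN; Protocol 12.3 already asks sites for the normal ranges of their local laboratories.
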